- h Ophthalmic assessment (performed by an ophthalmologist) will also be done as clinically indicated. Ophthalmic assessment includes visual acuity testing (including corrected distance acuity), slit lamp examination of the anterior eye segment, intraocular pressure, retinal OCT, and dilated fundoscopy. Additional examination methods such as specular microscopy and corneal pachymetry will be done as clinically indicated. Retinal OCT scans will be read locally and images will be provided to the OCT imaging vendor. Refer to the Study Manual for details regarding image collection and transfer or shipment. Ophthalmic assessment will be conducted at C13D28 or EOT visit unless performed within previous 4 weeks.
- i Full physical examination at screening, C1D1, and C13D28/EOT; abbreviated or symptom-directed physical examination at C2D1, C4D1, C7D1, C10D1, C13D1, every 6 months after EOT, and at the EOS visit.
- j For each subject, 12-lead ECGs will be done at Screening; predose on Day 1 of Cycles 1 and 2; and at C13D28 or EOT visit.
- k QOL assessments should be conducted before study drug administration, AE evaluation, and disease status notification, and preferably in order of EQ-5D-5L then EORTC QLQ-C30. Subjects should complete QOL assessments for 18 months; for subjects who complete all 52 weeks of study drug treatment, the last assessment will be at the first 6-month follow-up visit after discontinuation of study drug. Assessments do not need to be administered at the EOT visit if they were completed within the previous 7 days at a regularly scheduled visit.
- l Laboratory tests will be collected and analyzed on the scheduled day, even if study drug treatment is being withheld. Laboratory tests must be conducted within the windows specified in the protocol.
- m Hematology will be assessed at C1D1, C2D21, C4D21, C7D21, C10D21, C13D21, and C13D28 or EOT (refer to [Table 3](#)). Clinical chemistry will be assessed at C1D1, C1D4, C1D7, C1D14, C1D21; Cycles 2-13 (Day 21); and C13D28 or EOT (refer to [Table 3](#)).

The schedules for these clinical laboratory tests coincide, as closely as possible, with the blood draws specified for PK and cfDNA (refer to [Table 3](#)). Every attempt should be made to collect the clinical chemistry sample at the same time as the PK sample taken at 4 hours after study drug administration.

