3.4.1 Clinical Pharmacokinetics and Phase 1 Data

The PK of infigratinib and its active metabolites (BHS697, CQM157) have been evaluated following single and repeat daily doses in a Phase 1 study (CBGJ398X2101).

Following a single dose, median T_{max} was approximately 3-4 hours. Infigratinib had a relatively short median elimination half-life ranging from 2.69 to 5.71 hours on Day 1. Despite the relatively short half-life on Day 1, accumulation was observed with daily dosing at doses ≥ 60 mg, likely due to auto-inhibition of cytochrome P450 3A4 (CYP3A4) mediated clearance

pathways (data on file). Mean accumulation ratio (R_{acc}) ranged from 3 to 8 on Days 15 and 28. The interpatient variability was high for infigratinib.

In vitro studies indicated that infigratinib inhibits CYP3A4; therefore, a clinical drug-drug interaction study (QBGJ389-106) was conducted to assess the effects of multiple doses of infigratinib on midazolam (a sensitive CYP3A4 substrate). Midazolam exposure in terms of AUC_{inf} and C_{max} was minimally reduced (11% and 1%, respectively). For the active metabolite, 1-hydroxymidazolam, exposure increased by 19% and 26% for AUC_{inf} and C_{max} , respectively. Overall, these results indicate that infigratinib had a small effect on the metabolism of midazolam and can be considered a weak CYP3A4 inhibitor. As such, infigratinib is not expected to have a clinically relevant effect on drugs metabolized by CYP3A4. However, due to the weak inhibition, drugs that are CYP3A4 substrates and have a narrow therapeutic index should be co-administered with caution.

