Study drug	125 mg or matching placebo	100 mg or matching placebo	75 mg or matching placebo	50 mg or matching placebo

^a Dose reduction to 50 mg requires prospective sponsor medical monitor approval. Details are provided in the text above.

NOTE: The minimum daily dose of study drug allowed in the study is 50 mg.

Table 6: Criteria for Interruption and Re-initiation of Study Drug for Adverse Events Considered to be Possibly Related to Study Drug

Worst Toxicity CTCAE^a (version 5.0) Grade (Unless Otherwise Specified)	Dose Modifications any Time During a Cycle of Therapy
CARDIAC DISORDERS	
Cardiac – Prolonged QTcF Interval	
Grade 2: Average QTc 481 - 500 msec	
Maintain dose level of study drug.
 
Two additional ECGs separated by \geq5 minutes should be performed to confirm the finding. If the finding is confirmed, single ECG assessments should be performed for 2 additional cycles at the same frequency as in Cycle 1, or as clinically indicated. If abnormality is detected, 2 additional ECGs separated by at least 5 minutes should be performed to confirm the finding.
 
• If ECG assessments show no QTcF \geq481 msec, for subsequent cycles ECG monitoring will be performed according to the visit schedule.• If ECG assessments are still abnormal (QTcF \geq481 msec and \leq500 msec), then ECG monitoring must continue at the same frequency as in Cycle 1 for all subsequent cycles.

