9.4 Study Drug Dosing During Treatment Period (Days 1-28, Cycles 1-13)

Daily dosing of study drug using a 3 weeks on (Days 1-21)/1 week off (Days 22-28) schedule for each 28-day treatment cycle.

Study drug may be dispensed at study visits on Day 1 of C1, C2, C4, C7, C10, and C13 and/or monthly at study visits per local standard practice.

9.5 Study Visits During Treatment Period (Cycle 1 Day 1 to Cycle 13 Day 21)

The following assessments are to be performed during the Treatment Period as indicated below and as detailed in [Table 2](#) and [Table 3](#). Screening assessments conducted within 3 days before the first treatment can be used to satisfy the C1D1 requirement.

Throughout the treatment period, subjects will be monitored for AEs and concomitant medication use. Other safety assessments, including full or abbreviated/symptom-directed physical examinations; vital signs; ophthalmic assessments (performed by an ophthalmologist); laboratory measures (hematology, blood chemistry, coagulation, pregnancy) and urinalysis ; and 12-lead ECG will be conducted at the times indicated in [Table 2](#) and [Table 3](#). Laboratory tests will be collected and analyzed on the scheduled day, even if study drug is withheld.

The following assessments will be performed on C1D1, C2D1, C4D1, C7D1, C10D1, and C13D1, unless otherwise indicated:

- Quality of Life (QOL) assessments (before study drug administration).
- ECOG performance status.
- Ophthalmic assessment (C2D1, C4D1, C7D1, C10D1, C13D1, and if clinically indicated). Retinal optical coherence tomography (OCT) scan images will be read locally and images will be sent to the OCT imaging vendor. Refer to the Study Manual for details regarding image collection and transfer or shipment.
- Physical examination (full physical examination at C1D1, abbreviated or symptom-directed physical examination thereafter).
- Weight (and BMI determination).
- Vital signs.
- 12-lead ECG (predose on C1D1 and C2D1).
- If local programmed death-ligand 1 (PD-L1) testing is already known, record it (C1D1). If PD-L1 results are not known, and tissue was sent for testing, record the PD-L1 results as soon as available. While the PD-L1 results are not required for assessment of eligibility, testing for PD-L1 is required (it is not optional) (see [Section 10.3](#) for additional details).
- Blood draw:
 - Hematology will be assessed at the following timepoints:
 - Cycle 1 (Day 1).
 - Cycles 2, 4, 7, 10, and 13 (Day 21).

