Disease-free survival time is calculated as the number of months from randomization to the date of local/regional invasive or metastatic recurrence or death due to any cause (referred as DFS event) ((date of DFS event - date of randomization + 1)/ (365.25/12)). Subjects without recurrence (local/regional invasive or metastatic) or death will be censored at the last radiology assessment if previous cystoscopy result within 6 months is negative for muscle invasive disease, otherwise, DFS will be censored at the last complete recurrence assessment. Subjects who have no disease assessments after baseline will be censored on the randomization date. The primary DFS endpoint will be based on the central review (BICR), while for the secondary endpoint, the investigator reviewed DFS will be based on investigator review.

DFS including intraluminal low risk recurrence

The investigator reviewed DFS including intraluminal low risk recurrence is defined as the time from randomization to any recurrence as determined by investigator, or death due to any cause, whichever occurs earlier. For subjects without documented recurrence and are still alive, they will be censored at the last complete disease assessment (or, if no disease assessments are performed after the baseline visit or no death has been recorded, at the time of randomization).

Relative dose intensity

The relative dose intensity is defined as cumulative actual dose a subject have received divided by the planned cumulative dose. For example, a subject takes study drug from Day 1 to Day 21 at 125 mg/day; then from Day 29 to Day 30 at 100 mg/day, and end treatment afterward. The cumulative actual dose $=(21*125)+(100*2)=2825$ mg; the planned cumulative dose $=(21*125)+(125*2)=2875$ mg. The relative dose intensity $= 2825/2875=98.3\%$.

Study Day 1

Study Day 1 is defined as the day of the first administration of study treatment after randomization.

Treatment Duration

Treatment duration is defined as last dose date – first dose date +1.

On Treatment Period

On treatment period is defined as first administration of study treatment through 30 days after the last administration of study treatment inclusively.

Treatment-emergent Adverse Event

A treatment-emergent adverse event is defined as an adverse event that occurs on or after the first administration of study treatment and within 30 days after the last administration of study treatment.

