3. LVEF <20%

8.10.7 ECG

The electrocardiogram (ECG) summaries will include all assessments available for the ECG parameter collected no later than 30 days after the last study treatment administration date.

ECG parameters will be summarized at baseline, each post-baseline visit, the maximum and minimum observed post-baseline values, and last observed value, along with the change from baseline. For the maximum/minimum/last observed value, both scheduled and unscheduled assessments will be considered.

The number and percentage of subjects with notable ECG values will be presented.

- QT
 - New value of >500 ms
- QTcB, or QTcF
 - New value of >450 ms
 - New value of >480 ms
 - New value of >500 ms
 - Increase from baseline of >30 ms to \leq 60 ms
 - Increase from baseline of >60 ms
- Heart Rate (HR)
 - Increase from baseline >25% and to a value >100 bpm
 - Decrease from baseline >25% and to a value <50 bpm
- PR
 - Increase from baseline >25% and to a value >200 ms
- QRS
 - Increase from baseline >25% and to a value >100 ms

A listing of all ECG assessments will be produced by treatment and notable values will be flagged. In the listing, the on-treatment assessments will be flagged. In addition, a shift table baseline to worst on-treatment result for overall assessments will also be produced.

8.10.8 *Vital Signs and ECOG Performance Status*

Eastern Cooperative Oncology Group (ECOG) performance status will be summarized at baseline, each post-baseline visit (based on the visit schedule defined in the protocol along with a window), the worst observed post-baseline values, and the last observed value, along with the change from baseline.

Vital sign assessments are performed to characterize basic body function. The following parameters were collected: weight (kg), body temperature (°C), pulse rate (beats per minute), systolic and diastolic blood pressure (mmHg). The vital sign summaries will include all assessments available no later than 30 days after the last study treatment administration date. The vital sign will be summarized at baseline, each post-baseline visit, the maximum and minimum observed post-baseline values, and last observed value, along with the change from baseline.

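### Both fixed-time post-baseline ECGs fall at least 2 days after the last scheduled dose, yet the SAP reports them in its QTcF threshold and on-treatment shift tables without separating them

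*Protocol*

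**What the plan says.** **Dosing.** Protocol Section 9.4: "Daily dosing of study drug using a 3 weeks on (Days 1-21)/1 week off (Days 22-28) schedule".

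**ECGs.** Table 2, footnote j: "12-lead ECGs will be done at Screening; predose on Day 1 of Cycles 1 and 2; and at C13D28 or EOT visit". Section 9.5 repeats the timing: "12-lead ECG (predose on C1D1 and C2D1". The C2D1 window is minus 3 days only (Table 2, footnote e). The C13D28 visit has a window of plus or minus 5 days. After early discontinuation, the EOT visit is due within 5 days (Section 9.6).

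**Visits during dosing.** Every cycle has a Day 21 visit with PK draws before and 4 hours after a supervised dose (Table 3). Its minus-2-day window covers Days 19-21, all dosing days. Table 9 takes the 4-hour concentration as Cmax, and clinical chemistry is aligned with that draw (Table 2, footnote m). No ECG is scheduled there.

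**Follow-up of a QTc finding.** Protocol Table 6 says that, if ECGs are still abnormal, "ECG monitoring must continue at the same frequency as in Cycle 1 for all subsequent cycles".

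**Reporting.** SAP Section 6 defines the on-treatment period as first dose through 30 days after the last dose. SAP 8.10.7 applies the same 30-day limit to ECG summaries, counts QTcB or QTcF above 450, 480 and 500 ms and increases from baseline, and adds that "a shift table baseline to worst on-treatment result for overall assessments will also be produced". It makes no distinction by dosing day.

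**The concern.** A reader who sees few QTcF values above 480 or 500 ms, under an on-treatment label, will take that as evidence about subjects exposed to the drug. For a subject on the planned calendar, both fixed-time readings behind the table were taken when dosing had been stopped for days.

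Both arms follow the same calendar, so the timing does not favour either arm. But if a QTc effect tracks concentration and wanes in the off week, the difference from placebo shrinks towards zero. The table would then be uninformative about peak exposure while looking reassuring.

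Two features of the protocol make this worth raising. Medications with QT liability are permitted with caution and careful monitoring (Section 7.6.1), and the QTc actions in Table 6 depend on a prolongation being detected.

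**Working it through.** No sample size, power or alpha figure is involved. The check is calendar arithmetic plus a bounded estimate of residual drug.

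**1. Confirm the calendar from the plan's own figures.**
- 13 cycles × 28 days = 364 days = 52 weeks, the stated maximum treatment duration.
- The SAP Section 6 dose-intensity example reads "a subject takes study drug from Day 1 to Day 21 at 125 mg/day; then from Day 29 to Day 30 at 100 mg/day". Actual dose: 21×125 + 2×100 = 2825 mg. Planned dose: 21×125 + 2×125 = 2875 mg. The ratio is 98.3%, as the SAP states. The last dose of a cycle is therefore on Day 21 and the next on Day 29, which is C2D1.

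**2. Time from the last scheduled dose (Day 21) to each fixed-time post-baseline ECG.** Days are counted from Day 1 of the cycle containing that last dose.

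| ECG | Allowed days | Days since last dose | Hours |
|---|---|---|---|
| C2D1, predose | 26 to 29 | 5 to 8 | 120 to 192 |
| C13D28, ±5 days | 23 to 33 | 2 to 12 (nominal 7) | 48 to 288 (nominal 168) |

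The C1D1 predose ECG is a baseline. So 2 of 2 fixed-time post-baseline ECGs follow the end of dosing for the cycle, and neither is near the median Tmax of about 3-4 hours (Section 3.4.1).

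**3. Residual infigratinib at those times.** Fraction remaining = 2^(−h/t½), relative to the level at the start of decline.

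(a) *Day 1 half-life.* Section 3.4.1: "Infigratinib had a relatively short median elimination half-life ranging from 2.69 to 5.71 hours on Day 1".
- C2D1: from 120/5.71 = 21 to 192/2.69 = 71 half-lives, so essentially nil.
- C13D28 at its earliest (48 h): 8.4 to 17.8 half-lives, so below 0.3%.

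(b) *Assumed effective half-life.* Section 3.4.1 gives mean accumulation ratios R of 3 to 8. With constant clearance and 24-hour dosing, t½ = 24·ln2 / (−ln(1−1/R)). R = 3 gives 41 h and R = 8 gives 125 h.

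| Hours since dose | t½ = 41 h | t½ = 125 h |
|---|---|---|
| 48 (C13D28, earliest) | 44% | 77% |
| 120 (C2D1, earliest) | 13% | 51% |
| 168 (C13D28, nominal) | 6% | 39% |
| 192 (C2D1, nominal) | 4% | 34% |
| 288 (C13D28, latest) | 1% | 20% |

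At C2D1 the range is thus essentially nil under (a) and about 4-51% under (b).

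**4. Readings that can be close to a dose.** An early EOT visit comes 0-5 days after stopping. As an illustration, assume that the stopping day is uniform over the 28-day cycle. With the visit on the stopping day, 22/28 = 79% of visits are within 1 day of the last dose. With a 1-day lag it is 21/28 = 75%, and from a 2-day lag none are. The documents do not give the actual lags.

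**5. Table 6 against the schedule.** Cycle 1 contains one scheduled ECG, on Day 1 before the first dose. Read literally, follow-up at the Cycle 1 frequency is one ECG per cycle, with no defined relation to dosing. The wording does not say what is meant.

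**The case against.** **Points that stand.**
- *Low prior concern.* Section 7.6.1 says that preliminary data show no effect on cardiac conduction or ECG intervals, and Section 3.3 reports no electrocardiographic effect in nonclinical safety pharmacology. This does not make off-week readings informative, but it lowers the severity.
- *Other readings exist.* Early EOT ECGs can be close to a dose, and unscheduled ECGs enter the maximum, minimum and last values. Because the study closed early (SAP Section 1), EOT visits may be a sizeable share. That share is not stated.
- *Off drug is certain for dosing, not for exposure.* Section 3.4.1 attributes accumulation to probable auto-inhibition of clearance, which breaks the constant-clearance assumption in 3(b). Active metabolites exist, and no half-life is given for them.

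**A point that stands in part.** The SAP defines its on-treatment window openly and summarises ECG parameters by visit, so a careful reader can recover the timing there. The pooled threshold counts and the worst-value shift table do not allow this.

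**Stronger readings that the documents do not support.**
- *That the eye examinations share the defect.* Section 9.5 schedules "Ophthalmic assessment (C2D1, C4D1, C7D1, C10D1, C13D1, and if clinically indicated" with no predose rule, and Day 1 is a dosing day. An examination on nominal Day 1 may follow that day's dose. Only use of the minus window places it in the off week.
- *That eye results are labelled on-treatment.* SAP 8.10.5 describes them as post-baseline.
- *That retinal effects would be missed in most subjects.* Table 6 allows up to 14 days off drug for retinal and other ocular findings to resolve, so it contemplates findings that outlast the off week. Examinations are also required at any new visual disturbance (Section 10.5.7).

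**Conclusion.** The point holds for ECGs. On the planned calendar, both fixed-time post-baseline ECGs come after dosing has stopped for the cycle, by 5-8 days at C2D1 and by at least 2 days at C13D28. None is timed to peak exposure. The pooled QTcF threshold counts and the worst on-treatment shift table therefore say little about QTc at peak concentration, except through early EOT and unscheduled ECGs of unknown number.

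The calendar finding assumes only that subjects follow the planned 21-days-on, 7-days-off schedule without holds. The residual-exposure range (essentially nil, or about 4-51% at C2D1) rests on the half-life assumption, and the documents cannot narrow it. Severity is moderate to low. A reader might infer that the schedule hides a real QTc effect. Nothing in the documents shows such an effect; the defect is that the planned readings cannot speak to it.

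**What to change.** **Protocol (successor study or any remaining visits; measurement timing only).** Take the planned post-baseline ECGs at existing Day 21 visits beside the 4-hour PK draw, for example C1D21 in place of C2D1 and C13D21 in place of C13D28. Keep the EOT ECG for early discontinuation. The number of planned ECGs is unchanged. Reconcile the Table 6 wording on Cycle 1 frequency with the ECG schedule.

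**SAP 8.10.7 (still usable).** Derive time since last dose for each ECG and tabulate results by it. Identify off-week readings separately in the threshold and on-treatment shift tables. Dose changes and missed doses are recorded in the eCRF (Protocol Section 7.4), so the variable should be derivable at least to the day. At most, show eye results by the same variable in SAP 8.10.5; no relabelling is needed there.

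**Clinical study report.** State that the fixed-time post-baseline ECGs were scheduled after dosing had stopped for the cycle.

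**Cost.** A slightly longer Day 21 visit where the schedule can still change, and one derived variable. Because the study has closed, only the SAP change and the report statement apply to this trial.

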3 BACKGROUND

3.1 Overview of Disease Pathogenesis, Epidemiology and Current Treatment

3.1.1 *Upper Tract Urothelial Carcinomas*

In 2018, it was estimated that 150,350 new patients would be diagnosed with urinary system cancer: 81,190 urinary bladder; 65,340 kidney and renal pelvis; and 3820 ureter and other urinary organs. Excluding non-urothelial kidney cancers, approximately 5% to 10% of all urothelial carcinomas are upper tract urothelial carcinomas (UTUCs). The incidence of UTUC is 2 to 3 times greater in men than women ([Siegel 2018](#); [Roupret 2015](#)).

In contrast to invasive urinary bladder cancer (UBC), UTUC has a more aggressive clinical course. At the time of diagnosis, 60% of patients with UTUC have invasive cancer compared to 15% to 25% of patients with UBC ([Margulis 2009](#); [Roupret 2015](#)). Thirty-six percent (36%) have regional disease and 9% have distant disease ([Raman 2010](#)). A large retrospective review of 1363 patients with UTUC who underwent radical nephroureterectomy (RNU) at 12 centers demonstrated that 28% of the total population had recurrence outside of the bladder after RNU ([Margulis 2009](#)).

Standard-of-care neoadjuvant, adjuvant, and metastatic disease treatment is based on urothelial histology common to UBC and UTUC. Neoadjuvant and adjuvant treatment regimens containing cisplatin in combination with other cytotoxic agents are administered for 3 to 4 cycles. These regimens are: dose-dense methotrexate, vinblastine, doxorubicin, and cisplatin (DDMVAC); gemcitabine and cisplatin; and cisplatin, methotrexate, and vinblastine (CMV; National Comprehensive Cancer Network [[NCCN Guidelines Version 3 2018](#)]; European Society of Medical Oncology [[ESMO Guidelines](#)] [[Bellmunt 2014](#)]).

The peak incidence of UTUC occurs predominantly in 70- to 90-year-old patients who, if eligible for RNU, have 1 remaining kidney following surgery and often have other significant co-morbid conditions making cisplatin-based treatment a challenge ([Roupret 2015](#)). Renal function before and after RNU greatly limits the number of patients with UTUC who are eligible for platinum-based neoadjuvant or adjuvant therapy. Retrospective review of 336 patients with UTUC treated with RNU at the Cleveland Clinic using an estimated glomerular filtration rate (eGFR) cutoff of 60 mL/min/1.73 m² determined the percentage of patients eligible for platinum-based therapy. The median age was 72 years and the median preoperative eGFR was 59 mL/min/1.73m². Before RNU, 48% of patients were eligible for platinum-based therapy and after RNU 22% were eligible; for patients with Stage pT2 to pT4 and/or pN1 to pN3 disease these proportions were 40% and 24%, respectively ([Lane 2010](#); [Birtle 2018](#)).

The POUT study, a large randomized trial in UTUC supports the use of standard-of-care adjuvant platinum-based chemotherapy ([Birtle 2020](#)). Patients with histologically confirmed Stage pT2 to T4, N0-3, M0 UTUC, World Health Organization (WHO) performance status 0-1, ≤ 90 days post RNU were randomly assigned (1:1) to 4 cycles gemcitabine and cisplatin (or gemcitabine and carboplatin if their glomerular filtration rate (GFR) was 30-49 mL/min) versus surveillance. There were 260 patients (131 chemotherapy and 129 surveillance patients) in the

intent-to-treat (ITT) population. The distribution of patients by stage was: 28% Stage pT2; 66% pT3; and 91% pN0. The 3-year disease-free survival (DFS) was 71% for chemotherapy patients (95% confidence interval [CI]: 61, 78) and 46% for surveillance patients (95% CI: 36, 56). The metastasis-free survival (MFS) also favored the chemotherapy patients (HR=0.48 [95% CI: 0.31, 0.74; p=0.0007]). Subgroup analysis demonstrated benefit was greater for patients who received gemcitabine and cisplatin (HR 0.35 [95% CI: 0.20,0.61]) compared to patients who received gemcitabine and carboplatin (HR 0.66 [95% CI: 0.35,1.26]). The independent Data Monitoring Committee (DMC) recommended stopping enrollment because the study met the early stopping criteria for efficacy. Patients continue to be followed for OS.

3.1.2 *Invasive Urinary Bladder Carcinomas*

Approximately 20% of patients with urothelial carcinoma have invasive UBC at the time of diagnosis and only 15% to 25% of Stage T2 or higher invasive UBC tumors have activating FGFR3 alterations (Roupret 2015). Nonetheless, invasive UBC has a poor prognosis and approximately 50% of patients with invasive UBC will develop metastatic disease; 5-year mortality is approximately 50% (Knowles 2015). Phase 3 trials have demonstrated a survival benefit for neoadjuvant cisplatin-based chemotherapy; however, patients with residual disease following neoadjuvant therapy have a poor prognosis (Grossman 2003). In addition, studies suggest that patients with invasive UBC are unlikely to receive neoadjuvant or adjuvant cisplatin-based chemotherapy, in part due to cisplatin ineligibility (Porter 2011). Moreover, postoperative complications can preclude the use of adjuvant cisplatin-based therapy (Donat 2009). Therefore, patients with invasive UBC harboring FGFR3 alterations and either residual disease following neoadjuvant therapy or who are ineligible to receive or refuse cisplatin-based adjuvant chemotherapy will be permitted to enroll into this study. Given the small patient population, it is expected that $\leq 15\%$ of enrolled patients will have invasive UBC. (Note: No more than 15% of the population will be enrolled with UBC and $\leq 25\%$ of UTUC patients will have Stage pT2 UTUC [limit will be based on stratification]). The number of subjects refusing cisplatin-based perioperative therapy will be capped at approximately 10% of the total population (approximately 22 subjects).

3.1.3 *Overview of the FGFR Family and FGFR Genetic Alterations in Human Malignancies*

The fibroblast growth factor receptor (FGFR) family of receptor tyrosine kinases (RTKs) consists of 4 members (FGFR1, FGFR2, FGFR3, FGFR4) which serve as high affinity receptors for 22 different fibroblast growth factors (FGFs).

Several lines of evidence support the association and the involvement of FGFRs in human cancer, where genetic alterations leading to abnormal activation and/or deregulated expression of FGFs and FGFRs family members has been found in diverse tumor types.

Somatic activating mutations in FGFR3 have been identified in solid tumors, with high frequency in bladder carcinomas (Cappellen 1999), where FGFR3 overexpression is also reported (Tomlinson 2007). Activating point mutations of FGFR3 have been identified in approximately 40% of bladder tumors overall. Eleven different missense mutations in Exons 7,

10 and 15, have been identified (Knowles 2008). Some of these mutations lead to constitutive activation of the kinase activities of the receptor and downstream signaling, and activation of FGFR family members occurs also as fusion proteins that result from chromosomal rearrangements (eg, translocations) with other genes (Katoch 2019). FGFR1, FGFR2, and FGFR3 gene fusions or translocations (ie, rearrangements) have been identified in diverse cancer types including cholangiocarcinoma, breast cancer, prostate cancer, thyroid cancer, lung squamous cell carcinoma, bladder cancer, oral cancer, head and neck squamous cell carcinoma, and glioblastoma at low frequency (Wu 2013). As noted above, FGFR3 alterations occur in up to two-thirds of patients with UTUC (Sfakianos 2015; Moss 2017; Bagrodia 2019).

